### **6.3 Follow-up (Days 2 – 8): Visits 03 through 07**

#### **Clinic Visit 03, Day 2**

- Vital signs including oral temperature, blood pressure, and pulse will be obtained.
- A targeted physical exam may be performed, if indicated.
- Review concomitant medications
- Review for AEs and SAEs
- Counsel on need to avoid alcohol, drugs, tobacco and medications throughout the study.
- 10 mL of blood for oxfendazole and metabolites will be drawn at 24 (+ 8) hours.
- Spot urine for oxfendazole, metabolites will be collected at 24 (+8) hours.

#### **Clinic Visit 04, Day 3**

- Vital signs including oral temperature, blood pressure, and pulse will be obtained.
- A targeted physical exam may be performed, if indicated.
- Review concomitant medications
- Review for AEs and SAEs
- Counsel on need to avoid alcohol, drugs, tobacco and medications throughout the study.
- Collect 10 mL of blood for oxfendazole and metabolites.
- For the two sentinel subject only, collect 15 mL of blood for safety laboratory analysis (hemoglobin, white blood cell count with neutrophil and eosinophil count, platelet count, creatinine, Na, K, Cl, CO2, urea nitrogen, alanine aminotransferase (ALT), aspartate aminotransferase (AST), prothrombin time and partial thromboplastin time, total bilirubin).
- Spot urine for oxfendazole, metabolites will be collected between 48-60 hours.

#### **Clinic Visit 05, Day 4**

- Vital signs including oral temperature, blood pressure, and pulse will be obtained.
- A targeted physical exam may be performed, if indicated.
- Review concomitant medications
- Review for AEs and SAEs
- Counsel on need to avoid alcohol, drugs, tobacco and medications throughout the study.
- Collect 10 mL of blood for oxfendazole and metabolites.

- Collect 15 mL of blood for safety panels (hemoglobin, white blood cell count, including neutrophil and eosinophil counts, platelet count, prothrombin time, partial thromboplastin time, Na, K, Cl, CO2, urea nitrogen, creatinine, ALT, AST, total bilirubin, urine dipstick for protein and glucose) will be collected.
- An EKG will be performed. EKG will be reviewed by a cardiologist.

**Clinic Visit 06, Day 6 (+/- 1 day):**

- Vital signs including oral temperature, blood pressure, and pulse will be obtained.
- A targeted physical exam may be performed, if indicated.
- Review concomitant medications
- Review for AEs and SAEs
- Counsel on need to avoid alcohol, drugs, tobacco and medications throughout the study.
- Collect 10 mL of blood for oxfendazole and metabolites.

**Clinic Visit 07, Day 8 (+/-1 day):**

- Vital signs including oral temperature, blood pressure, and pulse will be obtained.
- A targeted physical exam may be performed, if indicated.
- Review concomitant medications
- Review for AEs and SAEs
- Counsel on need to avoid alcohol, drugs, tobacco and medications throughout the study.
- Collect 10 mL of blood for oxfendazole and metabolites.
- Collect 15 mL of blood for safety panels (hemoglobin, white blood cell count, including neutrophil and eosinophil counts, platelet count, prothrombin time, partial thromboplastin time, Na, K, Cl, CO2, urea nitrogen, creatinine, ALT, AST, total bilirubin, urine for dipstick testing for protein and glucose) will be collected.
- An EKG will be performed and will be reviewed by a cardiologist.

**6.4 Final Study Visit, Clinic Visit 08 (Day 15) (+/-2 days):**

- Vital signs including oral temperature, blood pressure, and pulse will be obtained.
- A targeted physical exam may be performed, if indicated.
- Review concomitant medications
- Review for AEs and SAEs
- Collect 10 mL of blood for oxfendazole and metabolites.
- Collect 15 mL of blood for safety panels (hemoglobin, white blood cell count, including neutrophil and eosinophil counts, platelet count, prothrombin time, partial thromboplastin time, Na, K, Cl, CO2, urea nitrogen, creatinine, ALT, AST, total bilirubin, urine for dipstick testing for protein and glucose) will be collected.
- An EKG will be performed and will be reviewed by a cardiologist.

**6.5 Early Termination Visit**

If a subject withdraws from the study early, the following procedures should be performed at the early termination visit.

- Review current health status (interim medical history) and note any changes since the last visit
- Review concomitant medications
- Blood will be collected for safety laboratory tests
- If early termination is prior to 72 hours after administration of the drug, urine will be obtained for PK studies
- A targeted physical examination may be performed, if indicated.
- Information regarding AEs and SAEs will be solicited. Any ongoing AEs or SAEs will be followed to resolution or until a stable chronic condition has been established.

Follow-up assessments will be completed according to the protocol schedule, if possible.

## 6.6 Unscheduled Visit

Unscheduled visits may occur at any time during the study. Unscheduled visits may occur after the scheduled final study visit (Day 15) if necessary to follow any AE occurring during the study period to resolution or stability. The procedures below are to be performed at any unscheduled visit. See the Manual of Procedures (MOP) for instructions on documentation and data reporting.

- Interim medical history will be reviewed.
- Review concomitant medications.
- Vital signs (P, BP, oral T), if clinically indicated will be obtained.
- A targeted physical exam, if indicated based on symptoms will be performed.
- Adverse events and serious adverse events will be reviewed.

## 6.7 Handling of Abnormal Liver Function or Hematological Tests

Preclinical tests demonstrated changes in liver function and hematological tests. Subjects demonstrating a grade 3 or higher change in hematological parameters of absolute neutrophil count, hemoglobin, or platelet count or ALT or AST greater than 3 times the upper limit of normal or total bilirubin greater than 2 x the upper limit of normal will be asked to return for repeat testing within 72 hours of detection of the abnormal laboratory test. Repeat testing of any change in the complete blood count or absolute neutrophil count will require a repeat CBC with differential. Any change in the mentioned liver function tests (ALT, AST, or total bilirubin) will require repeat evaluation of all 4 liver tests. Testing should be repeated 2-3x per week until the laboratory value stabilizes or has returned to normal. All of the evaluations listed under “unscheduled visits” will apply for these return visits that require additional laboratory testing.

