### 7.2 Laboratory Evaluations

#### 7.2.1 Clinical Laboratory Evaluations

Clinical laboratory evaluations will be performed by the University of Iowa Clinical Pathology Laboratory.

Specific tests to be performed are described below:

**Hematology** includes: hemoglobin, WBC count with differential (eosinophils, neutrophils), platelets, prothrombin time and partial thromboplastin time

**Clinical chemistry** includes: Na, K, Cl, CO2, urea nitrogen, creatinine, ALT, AST, total bilirubin

**Urinalysis** will be performed by dipstick testing for proteinuria and glucose in the research clinic. Confirmatory testing may be sent to the University of Iowa Clinical Pathology Laboratory for reflectance spectrophotometry analysis. Note: Urinalysis should be deferred if a participant is menstruating, but should be performed as soon as possible.

One or more of the laboratory parameters may be repeated at any time during the study as determined by the PI, if indicated by an AE. A clinically significant abnormal value should be repeated within 10 days if possible and followed up as clinically relevant.

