## **SUPPLEMENTS/APPENDICES**

**APPENDIX A: SCHEDULE OF EVENTS**

Study Visit Number	1	2	3	4	5	6	7	8
Study Day (post administration)	D-28 to -1	D1	D2	D3	D4	D6	D8	D15
Visit/Contact Window (Days)	NA	NA	NA	NA	NA	+/- 1	+/- 1	+/- 2
Informed Consent	x							
Inclusion/Exclusion	x	x						
Medical History	x							
Interim Medical History		x						
Concomitant Medications	x	x	x	x	x	x	x	x
Vital signs 	x	x	x	x	x	x	x	x
Physical Examination	x	x						
HIV, HBC, HCV Testing	x							
Administration of oxfendazole/placebo 		x						
Counseling on avoidance of medications, recreational drugs and alcohol intake	x	x	x	x	x	x	x	

Study Visit Number	1	2	3	4	5	6	7	8
Study Day (post administration)	D-28 to -1	D1	D2	D3	D4	D6	D8	D15
Visit/Contact Window (Days)	NA	NA	NA	NA	NA	+/- 1	+/- 1	+/- 2
Targeted physical exam			x	x	x	x	x	x
Screening and Safety Labs (CBC, Blood Chemistry, Urinalysis) 	x 	x 		X 	x 		x 	x 
EKG	x				x		x	x
Blood draw for oxfendazole and metabolites 		x	x	x	x	x	x	x
Urine collection for oxfendazole, metabolites and creatinine 		x	x	x				
Assess/review for AEs and SAEs		x	x	x	x	x	x	x
Blood Volume for Day (Total Blood Volume for Study)	15 mL (15mL)	105 mL (120mL)	10 mL (130 mL)	10 mL (140 mL)	25 mL (165 mL)	10 mL (175 mL)	25 mL (200 mL)	25 mL (225 mL)

 Vital signs and laboratory values will be evaluated using the FDA Guidance for Industry "Toxicity Grading Scale for Healthy Adult and Adolescent Volunteers Enrolled in Preventive Vaccine Clinical Trials," September 2007.

 Volunteers will remain fasting for 2 hours after administration of drug/placebo.

 Any abnormal laboratory result arising after administration of oxfendazole, and of moderate or greater severity, will be followed until results return to baseline value or for the duration of safety follow-up.

 Safety laboratories include: WBC, absolute neutrophil count, eosinophil count, total platelet count, hemoglobin, sodium, potassium, chloride, bicarbonate, urea nitrogen, creatinine, prothrombin time, partial thromboplastin time, ALT, AST, total bilirubin, urine dipstick for protein and glucose

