AST U/L	44 – 105	106-175	>175
ALT U/L	44 – 105	106-175	>175
Bilirubin (serum total) mg/dL	1.3 - 2.0	2.1 - 2.5	> 2.5
Bilirubin – when ALT $\geq$ 105 (Hy's law)	1.3 -1.5	1.6 – 2.0	> 2.0
Amylase- U/L	200-270	271-360	>360
Lipase- U/L	176-270	271-360	>360
Hemoglobin (Female) - g/dL	11.0 – 11.5	9.5 – 10.9	< 9.5
Hemoglobin (Male) - g/dL	12.0 – 12.5	10.0 – 11.9	<10.0
WBC Increase - cell/mm 	11,001 – 15,000	15,001 – 20,000	> 20,000
WBC Decrease - cell/mm 	2,500 – 3,500	1,500 – 2,499	< 1500
Lymphocytes Decrease - cell/mm 	750 – 1,000	500 – 749	< 500
Neutrophils Decrease - cell/mm 	1,500 – 2,000	1,000 – 1,499	< 1000
Eosinophils - cell/mm 	500-750	751-1500	> 1500
Platelets Decreased - cell/mm 	120,000 – 130,000	100,000 – 119,999	<100,000
PT – seconds (prothrombin time)	> ULN-14.4	14.5 – 15.7	> 15.7
PTT – seconds (partial thromboplastin time)	>ULN-42.1	42.2– 50.0	> 50.0
Fibrinogen increase - mg/dL	>ULN – 500	501 – 600	> 600
Fibrinogen decrease - mg/dL	<LLN – 140	125 – 139	<125
Urine *	Grade 1	Grade 2	Grade 3
Protein	1+	2+	>2+
Glucose	1+	2+	>2+
Blood (microscopic) - red blood cells per high power field (rbc/hpf)	5-10	11-50	> 50 and/or gross blood

\* The laboratory values provided in the tables serve as guidelines and are dependent upon institutional normal parameters.

\* Institutional normal reference ranges should be provided to demonstrate that they are appropriate.

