**APPENDIX D: UNIVERSITY OF IOWA NORMAL LABORATORY VALUES**

	Male	Female
Complete Blood Count		
WBC	3.7-10.5 k/mm 	3.7-10.5 k/mm 
RBC	4.5-6.2 millions/mm 	4.0-5.2 millions/mm 
Hemoglobin	13.2-17.7 g/dl	11.9-15.5 g/dl
Platelets	150-400 k/mm 	150-400 k/mm 
Hemogram plus Automated Differential		
Neutrophils	2188-7800/mm 	Same
Eosinophils	40-390/mm 	Same
BUN	10-20 mg/dl	Same
Creatinine	0.6-1.2 mg/dl	0.5-1.0 mg/dl
Alanine Aminotransferase (ALT)	0-41 u/l	0-33 u/l
Aspartate Aminotransaminase (AST)	0-40 u/l	0-32 u/l
Chloride	95-107	Same
CO 2	22-29 mEq/L	Same
Potassium	3.5-5.0	Same
Sodium	135-145	Same
Total Bilirubin	<=1.2 mg/dL	Same
Prothrombin Time	9-12 seconds	Same
Partial Thromboplastin Time	22-31 seconds	Same
Glucose (fasting)	65-99	Same
Urinalysis, Routine Screen (using Reflectance Spectrophotometry)	Specific gravity: 1.000-1.029; pH: 5.0-9.0, Dipstick negative for protein, hemoglobin, bilirubin, urobilinogen, ketones, glucose, leukocyte esterase and nitrite	Same
Urine Microscopy	0-5 WBC, 0-2 RBC	Same
Pregnancy Test		Positive = pregnant; Negative = not pregnant
Hepatitis B Surface Antigen	Negative	Same
HIV Types 1&2 Antibody	Non-Reactive	Same
Hepatitis C Virus Antibody, Version 2.0	Negative	Same

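### The liver triggers in Section 6.7 for a 72-hour repeat miss one narrow Grade 3 region: men with ALT 105-123, AST up to 120 and bilirubin 2.1-2.4, graded on the Hy's law row of Appendix B

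*Protocol*

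**What the plan says.** Section 6.7 of the protocol sets two kinds of trigger for a repeat within 72 hours of finding an abnormal result. For haematology the trigger is a grade: Grade 3 or above for neutrophils, haemoglobin or platelets. For the liver it is a multiple of the upper limit of normal (ULN): "ALT or AST greater than 3 times the upper limit of normal or total bilirubin greater than 2 x the upper limit of normal". After the first repeat, "Testing should be repeated 2-3x per week until the laboratory value stabilizes or has returned to normal". A change in ALT, AST or total bilirubin "will require repeat evaluation of all 4 liver tests", although only those three are named.

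Appendix B grades ALT and AST as 3 above 175 U/L and total bilirubin as 3 above 2.5 mg/dL. A separate Hy's law row lowers the Grade 3 bilirubin threshold to above 2.0 when ALT is 105 or more. A footnote adds that "The laboratory values provided in the tables serve as guidelines and are dependent upon institutional normal parameters". Appendix D gives the site's normal ranges by sex.

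Other follow-up provisions apply:

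- **Appendix A, third footnote:** "Any abnormal laboratory result arising after administration of oxfendazole, and of moderate or greater severity, will be followed until results return to baseline value". Alternatively, follow-up lasts as long as the safety period.
- **Section 7.2.1:** laboratory tests "may be repeated at any time during the study as determined by the PI, if indicated by an AE". In addition, "A clinically significant abnormal value should be repeated within 10 days if possible and followed up as clinically relevant".
- **Sections 8.2.1 and 8.4:** adverse events are followed until they resolve or stabilise, past the end of the study if need be.
- **Section 8.5:** a Grade 3 laboratory abnormality judged drug-related halts the study for review by the Safety Monitoring Committee (SMC).

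**The concern.** Sections 2.1.1.4 and 2.3.1 name liver and bone marrow as the principal target organs, and this is the first use of oxfendazole in humans. The Hy's law row shows that the protocol treats raised bilirubin as more serious when ALT is raised with it. Section 6.7 has no matching combined criterion, and its grade-based trigger does not extend to the liver. The pattern that Appendix B grades more strictly could therefore be the one Grade 3 liver result without mandatory early retesting. The stake is the follow-up of an individual subject: whether a joint rise in ALT and bilirubin is tracked closely by rule or only at the investigator's discretion.

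**Working it through.** The plan states no figure to reproduce here. The check compares two sets of thresholds.

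**Step 1. Turn the Section 6.7 multiples into values, using the Appendix D limits.**

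| Test | ULN, men | Trigger, men | ULN, women | Trigger, women |
|---|---|---|---|---|
| ALT (U/L) | 41 | > 3 × 41 = 123 | 33 | > 3 × 33 = 99 |
| AST (U/L) | 40 | > 3 × 40 = 120 | 32 | > 3 × 32 = 96 |
| Total bilirubin (mg/dL) | 1.2 | > 2 × 1.2 = 2.4 | 1.2 | > 2 × 1.2 = 2.4 |

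**Step 2. Compare each Appendix B Grade 3 row with these triggers.**

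- ALT > 175 is above 123 and 99, so it is covered for both sexes.
- AST > 175 is above 120 and 96, so it is covered.
- Bilirubin > 2.5 is above 2.4, so it is covered.
- Bilirubin > 2.0 with ALT ≥ 105:
  - Women: ALT ≥ 105 already exceeds 99, so it is covered.
  - Men: it is not covered when ALT is 105 to 123, AST is at most 120 and bilirubin is above 2.0 but no higher than 2.4.

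**Step 3. Size of the region.** At reporting precision there are 123 − 105 + 1 = 19 ALT values and 4 bilirubin values (2.1, 2.2, 2.3, 2.4), giving 19 × 4 = 76 pairs, each with AST at or below 120. A full enumeration (ALT and AST from 0 to 249 in steps of 1, bilirubin from 0 to 3.9 in steps of 0.1) found exactly this region for men and nothing for women.

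**Step 4. Time to the next scheduled liver test, if nothing else prompts one.**

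| First abnormal value | Next scheduled test | Interval |
|---|---|---|
| Day 3 (sentinels only) | Day 4 | 1 day |
| Day 4 | Day 8 ± 1 | 7 − 4 = 3 to 9 − 4 = 5 days |
| Day 8 ± 1 | Day 15 ± 2 | 13 − 9 = 4 to 17 − 7 = 10 days; nominally 7 |
| Day 15 ± 2 | none | – |

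The Section 6.7 rule would give 72 hours from detection.

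**Step 5. Sensitivity to the limits.** Section 6.7 does not say which ULN applies; Appendix D is the only list of site limits. The alternatives below are assumptions.

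- ULN 35, at which 105 and 175 are exactly 3 and 5 times the limit: the gap shrinks to ALT = 105.
- ULN 43 or 44 for both sexes (screening requires ALT and AST below 44): the gap widens to ALT 105-129 (3 × 43) or 105-132 (3 × 44) and includes women.
- Appendix B cut-off rescaled from 105 to 3 × 41 = 123 for men: only ALT = 123 remains.

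**The case against.** The arithmetic is not in dispute. The case against acting on it runs as follows.

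- **Follow-up is already mandatory.** Sections 8.2.1 and 8.4 require adverse events to be followed to resolution, beyond Day 15 if necessary. For a laboratory event that means repeat testing. This stands, and it means a Day 15 case is not abandoned. But those sections set no interval. The 10-day rule in Section 7.2.1 is looser than 72 hours, and the list of unscheduled-visit procedures in Section 6.6 contains no laboratory test.
- **The strongest consequence is in place.** A related Grade 3 laboratory result halts the study, as does disagreement within the Safety Review Committee about relatedness. This also stands, and it is why the point does not touch halting. It still sets no retest time for the affected subject.
- **Section 6.7 could be read more widely.** Its sentence on any change in ALT, AST or bilirubin might itself require repeat testing. That reading would make the numerical thresholds pointless. The parallel sentence on blood counts likewise says which tests to rerun, not when, so this objection fails.
- **Appendix B values are guidelines.** A site that scaled the ALT cut-off to its own limit would almost close the gap. No passage tells it to do so.
- **Nothing says repeat triggers must mirror grades.** True, and the liver triggers are stricter than the single-test Grade 3 rows. That makes the one uncovered row look like an oversight rather than a choice, and no reason is given for it.
- **The practical loss is small.** For a Day 4 value, 3 to 5 days is close to 72 hours plus result turnaround. The difference matters mainly for Day 8 and Day 15 values. This stands.

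**Conclusion.** The concern holds. Using the Appendix D limits and Appendix B as written, Section 6.7 leaves one Grade 3 liver region without a mandatory 72-hour repeat or testing two to three times a week: men with ALT 105-123, AST up to 120 and bilirubin 2.1-2.4. Every other Grade 3 ALT, AST or bilirubin result triggers both. The exact boundaries, and the absence of a gap for women, depend on the Appendix D limits.

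The gap is narrow. The documents give no rate for this pattern, at most 56 subjects receive drug, and an attentive investigator would probably retest anyway. It affects follow-up of an individual subject only. It still merits correction, because it concerns a named target organ in a first-in-human trial and the remedy is very cheap.

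**What to change.** Add one clause to the liver triggers in Section 6.7: any Grade 3 liver result in Appendix B, including total bilirubin above 2.0 mg/dL when ALT is 105 U/L or more, leads to the same 72-hour repeat and serial testing. This empties the uncovered region by construction, whichever ULN the site applies. The cost is one clause and an occasional extra blood draw in a subject who meets the added trigger.

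In the same edit, as a purely clerical matter, change the count of four liver tests in Section 6.7 to the three named, or name the fourth.

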## 7 STUDY PROCEDURES/EVALUATIONS

### 7.1 Clinical Evaluations

**Medical History:** Will be obtained by interview of the subjects. Subjects will be queried regarding a history of significant medical disorders of the head, eyes, ears, nose, throat, mouth, cardiovascular system, lungs, gastrointestinal tract, liver, pancreas, kidney, nervous system, blood, lymph glands, endocrine system, musculoskeletal system, skin, and genital/reproductive tract. A history of any allergies, cancer, immunodeficiency, psychiatric illness, substance abuse, and autoimmune disease will be solicited.

**Concomitant Medications:** All current medications and medications taken in the 30 days before enrollment (prescription and over-the-counter drugs) will be documented, as well as vitamins and supplements, through 14 days after receipt of study product. Assessment of eligibility also will include a review of prohibited medications (per the exclusion criteria).

**Physical Examination:** This examination will be conducted at Screening and Visit 2 and will assess general appearance including height and weight (at Screening only), vital signs (blood pressure, temperature, pulse), and the following areas/symptoms: skin, lymph nodes, head, eyes, ears, nose, throat, respiratory, cardiovascular, abdomen, extremities, musculoskeletal, and neurological.

**Vital Signs and Targeted Physical Examination:** Vital signs will be collected at each study visit. A targeted physical examination may be conducted at any study visit based on interim medical history.

**Adverse Events Assessments:** Subjects will be asked if they have any new symptoms since the prior visit.

### 7.2 Laboratory Evaluations

#### 7.2.1 Clinical Laboratory Evaluations

Clinical laboratory evaluations will be performed by the University of Iowa Clinical Pathology Laboratory.

Specific tests to be performed are described below:

**Hematology** includes: hemoglobin, WBC count with differential (eosinophils, neutrophils), platelets, prothrombin time and partial thromboplastin time

**Clinical chemistry** includes: Na, K, Cl, CO2, urea nitrogen, creatinine, ALT, AST, total bilirubin

**Urinalysis** will be performed by dipstick testing for proteinuria and glucose in the research clinic. Confirmatory testing may be sent to the University of Iowa Clinical Pathology Laboratory for reflectance spectrophotometry analysis. Note: Urinalysis should be deferred if a participant is menstruating, but should be performed as soon as possible.

One or more of the laboratory parameters may be repeated at any time during the study as determined by the PI, if indicated by an AE. A clinically significant abnormal value should be repeated within 10 days if possible and followed up as clinically relevant.

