#### **2.1.1.5 Animal Safety**

The potential cardiovascular or toxicity effects of oxfendazole (OXF) were investigated after drug administration to beagle dogs (22). Following administration of single oral doses of oxfendazole at 0, 5, 25 or 100 mg/kg, no changes in body weight, body temperature, clinical laboratory evaluations (hematology, serum chemistry, and coagulation studies), changes in vital signs (blood pressure, heart rate) or changes in electrocardiogram evaluations were noted.

[figure not shown]
A two week toxicology study of oxfendazole administered orally to rats at doses from 0-200 mg/kg, was recently performed (23). There were no changes in feeding, behavior or physiological measurements (23). Animals in the highest dose groups were euthanized on day 8 because of severe toxicity and mortality. Females had a higher incidence of mortality and more severe adverse effects than did males administered the same dose; correspondingly higher OXF exposure was found in females than in males. At the higher doses, WBC depletion was dose related, being severe in females at the highest dose. WBC recovered when OXF administration was suspended. Target organs of toxicity were bone marrow, epididymis, liver, spleen, testis and thymus. Hepatic midzonal fatty change was present in male and female rats administered the higher doses; these changes were still present after a 14-day recovery period. However, no effects on liver enzymes were seen in the clinical chemistry results, suggesting that these effects did not result in overt hepatotoxicity or compromised hepatic function; therefore, the toxicologic significance of this observation is unclear.

Several toxicology studies were performed at the time of Synanthic® approval. In single dose toxicology studies in mice, rats and dogs. One rat that received a dose of 6400 mg/kg, orally died from enteropathy. In subchronic toxicology studies in which rats and dogs were dosed over a two week period at doses ranging from 11-200 mg/kg, orally, decreases in neutrophil count, hemoglobin and hematocrit were seen at the higher doses, as were pathological changes in the liver (with hepatocyte vacuolation), gastroenteropathy, testes, bone marrow, liver, spleen,

and thymus. Toxicology studies demonstrated mild hepatotoxicity in rats fed 2.1 or 7 mg/kg daily for a year (21). Similar dog studies showed no toxicity (21). Fetotoxicity was noted in rats and mice (21).

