10. Any condition that would, in the opinion of the investigator, place them at an unacceptable risk of injury, render them unable to meet the requirements of the protocol, or that may interfere with successful completion of the study.
11. A history of alcohol consumption\* or any illicit drug use†, or history of substance abuse#. Individuals must agree to abstain from drug or alcohol use for 48 hours prior to enrollment through day 15. .

\*Greater than 7 alcoholic drinks per week. .

†Other than occasional marijuana use (less than once per week for the past 60 days is acceptable).

#Alcohol or illicit drugs within the past 3 years.

12. History of chronic tobacco use in the past 60 days.\*

\*A history of occasional tobacco use (less than 1 pack per week on average) is acceptable. Individuals will be counseled to abstain from use of tobacco and marijuana from screening through day 15.

Vital signs may be performed up to three times to allow for transient conditions to resolve. Screening laboratory values that are abnormal, but are considered to be abnormal due to an acute illness or process may be repeated once. Creatinine, AST, ALT, bilirubin and eosinophil count values that fall below normal values specified in the DMID Toxicity Table are not considered abnormal for the purposes of this study. Additionally, abnormalities in the RBC parameters other than hemoglobin and abnormalities in the WBC differential not specified in the inclusion criteria above (e.g. low basophils or eosinophils) will not be considered exclusionary

for this study and will be followed with the standard safety laboratory follow-up outlined in the study. Laboratory values that are performed as a standard panel by the clinical laboratory, but are not requested for the study, will be reviewed by a licensed study clinician and the clinician will determine whether the laboratory abnormality is clinically significant and should be considered exclusionary. If determined to be clinically insignificant, the study team is not required to follow the laboratory until resolution or the value is determined to be clinically stable.

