 Blood will be drawn prior to dosing for baseline PK data, and then at, 1, 2, 4, 6, 8, 10, 12, 24 (+ 8 hours), and on Day 3, followed by the indicated visit days. Blood will also be drawn at the final study visit (Day 15).

 Urine will be obtained on admission for baseline PK data, and all urine will be collected for the first 24 hours following the schedule of urine collections at 0-4, 4-8, 8-12, 12-24 hours. Spot urine samples will be collected on Days 2 and 3 following drug administration. A urine creatinine value will be tested on the 12-24 hours sample only.

 Screening labs include WBC, absolute neutrophil count, eosinophil count, total platelet count, hemoglobin, creatinine, ALT, AST, total bilirubin, random glucose, urine dipstick for protein and glucose

 Blood for safety laboratory analysis will be obtained for the two sentinel subjects in each dose group. (WBC, absolute neutrophil count, eosinophil count, total platelet count, hemoglobin, sodium, potassium, chloride, bicarbonate, urea nitrogen, creatinine, prothrombin time, partial thromboplastin time, ALT, AST, total bilirubin)

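### The safety laboratory lists omit the lymphocyte count although thymus, spleen and bone marrow were target organs in rats; adding it is a cheap improvement

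*Protocol*

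**What the plan says.** **Tests requested.** Section 7.2.1 gives the hematology panel as "hemoglobin, WBC count with differential (eosinophils, neutrophils), platelets, prothrombin time and partial thromboplastin time". Appendix A repeats the restriction. Footnote 4, for the scheduled safety draws, begins "Safety laboratories include: WBC, absolute neutrophil count, eosinophil count, total platelet count, hemoglobin". Footnote 8, for the two sentinel subjects on Day 3, lists "WBC, absolute neutrophil count, eosinophil count, total platelet count, hemoglobin, sodium, potassium, chloride, bicarbonate, urea nitrogen, creatinine, prothrombin time" and further coagulation and liver tests. Footnote 7, for screening, names the same cell counts. The Day 15 list in Section 6.4 reads "hemoglobin, white blood cell count, including neutrophil and eosinophil counts, platelet count, prothrombin time, partial thromboplastin time", followed by chemistry and dipstick tests. Section 4 and Sections 6.1 to 6.3 agree. Appendix D gives differential reference ranges for neutrophils and eosinophils only.

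**Animal findings.** For the two-week oral rat study (0 to 200 mg/kg), Section 2.1.1.5 says "Target organs of toxicity were bone marrow, epididymis, liver, spleen, testis and thymus". It also reports dose-related WBC depletion at the higher doses, with recovery once dosing was suspended.

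**Grades and rules.** Appendix B has a row "Lymphocytes Decrease": Grade 1 is 750 to 1,000, Grade 2 is 500 to 749, and Grade 3 is below 500 cells/mm³. Section 8.5 halts the study for SMC review on any Grade 3 laboratory abnormality deemed related to drug, without naming analytes. Section 6.7 asks for repeat hematology testing on Grade 3 changes in neutrophils, hemoglobin or platelets.

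**Unlisted values.** Section 4.2 has a clinician review "Laboratory values that are performed as a standard panel by the clinical laboratory, but are not requested for the study" and decide whether they should exclude the subject. After dosing, Section 8.2.1 lets an abnormal laboratory finding be an adverse event. Section 8.2.4 asks for abnormal laboratory values to be documented, reported and followed. Appendix A footnote 3 asks for follow-up of post-dose abnormalities of moderate or greater severity.

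**The concern.** The primary objective is safety in a first-in-human dose escalation, and the primary endpoint is the rate of related adverse events over 14 days. Laboratory grades also feed the release of each cohort after its sentinels, the review between cohorts and the halting rules. All of these work on values that someone has obtained and looked at.

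Three of the organs found to be targets in rats are lymphoid or blood-forming, yet the one white-cell line most closely tied to thymus and spleen is not a requested test. If total WBC and neutrophils tracked lymphocytes closely, this would not matter. The question is whether a marked lymphocyte fall can leave both of them unremarkable, and whether other text would then ensure that it is recorded.

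**Working it through.** The plan gives no figure for this point, so there is none to reproduce. The check has two parts.

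**1. The lists side by side**

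| Place | White-cell tests named | Lymphocytes |
|---|---|---|
| Section 4, screening to Day 15 | WBC, neutrophils, eosinophils | no |
| Sections 6.1 to 6.4 | the same | no |
| Section 7.2.1 | the same | no |
| Appendix A footnotes 4, 7 and 8 | the same | no |
| Section 6.7 repeat-test trigger | neutrophils (with hemoglobin and platelets) | no |

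**2. Can Grade 3 lymphocytes coexist with normal recorded values?**

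Inputs from the documents (per mm³):
- Appendix D normal ranges: WBC 3,700 to 10,500; neutrophils (N) 2,188 to 7,800; eosinophils (E) 40 to 390.
- Appendix B: lymphocyte (L) Grade 3 below 500; WBC decrease Grade 1 is 2,500 to 3,500.

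Assumption: monocytes plus basophils (M) lie between 0 and 800. The documents give no figure.

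Formula: WBC = N + E + L + M.

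Set L = 499, just inside Grade 3, and let N and E range over normal values:
- Lowest WBC: 2,188 + 40 + 499 + 0 = 2,727, which is WBC Grade 1.
- Highest WBC: 7,800 + 390 + 499 + 800 = 9,489, which is normal.

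Neutrophils needed for WBC to look normal (at least 3,700):
- E = 40, M = 0: 3,700 − 40 − 499 − 0 = 3,161.
- E = 390, M = 800: 3,700 − 390 − 499 − 800 = 2,011, so any normal neutrophil count (2,188 or more) is enough.

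Neutrophils needed for WBC to escape a grade (above 3,500):
- E = 40, M = 0: 3,501 − 40 − 499 − 0 = 2,962.
- E = 390, M = 800: 3,501 − 390 − 499 − 800 = 1,812, so again any normal count is enough.

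Over the assumed range, then, neutrophils of about 2,188 to 3,161 or more hide the fall from the WBC reference range. About 2,188 to 2,962 or more hide it from the WBC grade. Both thresholds lie low in the normal neutrophil range.

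**Illustration (all counts assumed).** N = 3,500, E = 150, M = 400, and L falls from 2,000 to 400:
- WBC before: 3,500 + 150 + 2,000 + 400 = 6,050.
- WBC after: 3,500 + 150 + 400 + 400 = 4,450.

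WBC, neutrophils and eosinophils are normal throughout, while lymphocytes reach Grade 3.

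**Can the recorded values recover it?** The remainder WBC − N − E equals L + M. It goes from 6,050 − 3,500 − 150 = 2,400 to 4,450 − 3,500 − 150 = 800. The drop is visible to anyone who computes it, but the plan does not ask for it and it cannot be graded. A remainder of 800 fits lymphocytes of 800 (Grade 1) as well as 400 (Grade 3).

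**The case against.** **The animal signal is indirect.** The documents nowhere report lymphopenia. The organ findings come from repeat dosing, whereas each subject here gets one dose. Single doses up to 100 mg/kg in dogs changed no hematology. Sections 2.1.1.4 and 2.3.1 name bone marrow and liver as the principal targets, and the older two-week studies report falls in neutrophils and hemoglobin, both of which are measured. All of this stands. A reader might infer that the animal data predict a lymphocyte effect; they make one plausible and no more.

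**A low count could still be captured.** A differential is ordered, Appendix D calls it automated, and Section 4.2 mentions basophils, which are on no list, so staff may well see unlisted values. Sections 8.2.1, 8.2.4 and 8.5 and Appendix A footnote 3 are not confined to listed analytes. A reader might infer that a Grade 3 fall would yield no recorded event at all. The documents do not support that: a value that is reported and noticed could be graded, recorded and brought under the halting rule. What remains is that no text requires the count to be requested or recorded, at baseline or after dosing.

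**Section 4.2 does not discard such values.** A reader might take it to place unrequested results outside the study data. It concerns eligibility, requires clinician review, and sends unlisted differential abnormalities to the standard laboratory follow-up. It therefore says nothing against recording post-dose values, although that follow-up does not request lymphocytes either.

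**Appendix B is generic.** It also grades calcium, magnesium, CPK, albumin, amylase, lipase and fibrinogen, none of which is ordered. The lymphocyte row alone therefore shows no inconsistency. It matters here only because it supplies a ready grade.

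**Conclusion.** The point holds as a cheap improvement to safety ascertainment, not as an error in the plan. The omission is consistent across the laboratory lists, and the rat target organs give a reason to measure lymphocytes.

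The size is a possibility, not a rate. Lymphocytes below 500/mm³ are compatible with normal WBC, neutrophils and eosinophils once neutrophils reach about 2,188 to 3,161/mm³, depending on eosinophils and on the assumed 0 to 800/mm³ of monocytes plus basophils. A fall that brings WBC to 3,500/mm³ or less would be graded through WBC. The documents do not allow an estimate of how often a selective fall would occur after one dose, and the illustration should not be read as one.

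As written, such a fall reaches the adverse event rate or the Grade 3 laboratory review only through an unrequested value being noticed and handled under general text. That is less reliable than scheduled recording and may differ between subjects and cohorts.

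**What to change.** Add the absolute lymphocyte count, taken from the differential already ordered, to Section 7.2.1, to Appendix A footnotes 4, 7 and 8, and to the lists in Section 4 and Sections 6.1 to 6.4. It would then be recorded at screening, at Day 1 baseline and at each later safety draw, and graded with the existing Appendix B row. Add the local reference range to Appendix D.

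Reconcile the laboratory lists with Sections 6.7 and 8.5, so that the protocol states whether and how a graded lymphocyte value falls under each. That choice is the sponsor's. If the omission is deliberate, say so and give the reason.

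**Cost.** Protocol wording and a data field. With safety or screening draws at screening and Days 1, 4, 8 and 15, plus Day 3 for two sentinels in each of seven cohorts, a full trial of 70 adds 70 × 5 + 7 × 2 = 364 recorded values, apart from screening failures and repeat tests. No extra blood or visit is needed, provided the laboratory's differential reports lymphocytes. The data forms and the manual of procedures are not among the documents and should be checked. The downside is a few incidental low-grade abnormalities to review.
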